### **3.5.3 Rabies Vaccine RVa (Chicken Fibroblast Rabies Vaccine RabAvert®)**

The 1 mL dose of the chicken fibroblast rabies vaccine should be administered on the LEFT side of the body in Left deltoid muscle or in the Left vastus lateralis (thigh) or rectus femoris (thigh). Five doses of the vaccine should be administered on Study Days 0, 3, 7, 14 and 28. The vaccine should be administered as soon as possible after dose constitution. RVa should be administered within 75 minutes after Study Drug.

### **3.5.4 Rabies Vaccine RVi (Human Diploid Cell Rabies Vaccine Imovax®)**

The 1 mL dose of the human diploid cell rabies vaccine should be administered on the LEFT side of the body in Left deltoid muscle or in the Left vastus lateralis (thigh) or rectus femoris (thigh). Five doses of the vaccine should be administered on Study Days 0, 3, 7, 14 and 28. The vaccine should be administered as soon as possible after dose constitution. RVi should be administered within 75 minutes after Study Drug.

## **3.6 Study Evaluations**

### **3.6.1 Efficacy Evaluations**

This is not an efficacy trial. A pharmacodynamic measurement of serum rabies virus neutralizing activity in international units will be used as a surrogate of protection. Refer to Table 3.11 for the day on which rabies virus neutralizing activity should be drawn. Refer to the Analytical methodology information sheet (provided under separate cover) for further instructions and additional information on specimen collection and processing.

### **3.6.2 Immunology Laboratory Evaluations**

A summary of immunologic assays to be performed on blood specimens is shown in Table 3.6-2. Staff at the clinical research site will refer to the most current version of the analytical methodology information sheet (provided under separate cover) for further instructions and additional information on specimen collection and processing.

**Table 3.6-2 Summary of Immunology Laboratory Evaluations**

Sample type	Assay	Study Days
Serum for pharmacokinetics	SYN023 concentration	0, 1, 3, 7, 14, 28, 35, 42, 84
Serum for anti-SYN023 antibodies	Anti-SYN023 antibodies	0,7,14, 28, 35, 42, 84, 112

### 3.6.3 Safety Evaluations

Electrocardiograms are performed to monitor subject safety (Table 3.1-1). Laboratory evaluations for subject safety are clinical chemistry evaluations, CBC, platelet counts and differential counts, PT(INR) an PTT and urinalyses, Please refer to Table 3.1-1 for a list of laboratory tests for monitoring of safety. Additional laboratory tests may be required for evaluation of specific adverse events such as anaphylaxis and immune complex diseases (see chapters 3.6.3.2)

#### 3.6.3.1 Pre-Study Study Drug and Post-Study Drug Administration Clinical Monitoring of Subjects

Hypersensitivity reactions are a potential adverse effect of all medicinal products administered in this protocol including monoclonal antibodies. Allergic reactions to vaccination are possible, therefore, appropriate drugs and medical equipment to treat acute anaphylactic reactions must be immediately available and a medically qualified study team member trained to recognize and treat anaphylaxis must be present in the clinic during the entire vaccination procedure and post-vaccination monitoring period. Appropriate drugs include intravenous fluids, epinephrine, antihistamines, corticosteroids, inhaled oxygen and drugs required for the treatment of cardiac arrest such as antiarrhythmics and pressors. Appropriate equipment includes devices for blood pressure monitoring, oximetry, maintenance of airway and intratracheal intubation and, removal of secretions and cardiac defibrillation.

Grade  $\geq 3$  hypersensitivity reactions are Immediately Reportable Events.

Subjects will have vital signs and oximetry taken prior to Study Drug administration. Before after and between each medicinal product administration vital signs and oximetry will be monitored every 30 minutes At every clinical contact the subject will be asked how they are feeling and if they have noticed any new adverse symptoms or manifestations.

Subjects will remain in the clinic under close observation for at least 240 minutes after receiving rabies vaccination that is administered after Study Drug. Vital signs and oximetry will be repeated every 30 minutes during the 240 minute monitoring period before subjects leave the clinic.

#### 3.6.3.2 Recognition of Anaphylaxis

When the diagnosis of anaphylaxis is considered the following laboratory tests should be obtained: plasma tryptase, plasma histamine and urinary N-

methyl histamine. Anaphylaxis is highly likely when any one of the following 3 criteria are fulfilled (Sampson et al. 2006):

- Acute onset of an illness (minutes to several hours) with involvement of the skin, mucosal tissue, or both (e.g., generalized hives, pruritus or flushing, swollen lips-tongue-uvula)

*AND AT LEAST ONE OF THE FOLLOWING*

- Respiratory compromise (e.g., dyspnea, wheeze-bronchospasm, stridor, reduced PEF, hypoxemia)
- Reduced BP or associated symptoms of end-organ dysfunction (e.g., hypotonia [collapse], syncope, incontinence)
- Two or more of the following that occur rapidly after exposure to a *likely allergen for that patient* (minutes to several hours):
  - Involvement of the skin-mucosal tissue (e.g., generalized hives, itch-flush, swollen lips-tongue-uvula)
  - Respiratory compromise (e.g., dyspnea, wheeze-bronchospasm, stridor, reduced PEF, hypoxemia)
  - Reduced BP or associated symptoms (e.g., hypotonia [collapse], syncope, incontinence)
  - Persistent gastrointestinal symptoms (e.g., crampy abdominal pain, vomiting)
- Reduced BP after exposure to *known allergen for that patient* (minutes to several hours):
  - Infants and children: low systolic BP (age specific) or greater than 30% decrease in systolic BP
  - Adults: systolic BP of less than 90 mm Hg or greater than 30% decrease from that person's baseline

### **3.6.3.3 Treatment of Anaphylaxis**

Epinephrine is the treatment of choice for anaphylaxis. Aqueous epinephrine, 0.01 mg/kg (maximum dose, 1.5 mg) administered intramuscularly every 5 to 15 minutes as necessary, is the recommended dosage for controlling symptoms and maintaining blood pressure. The 5-minute interval between injections can be liberalized to permit more frequent injections if deemed necessary by the clinician. Epinephrine may be administered subcutaneously or intramuscularly.

Intramuscular administration of injectable epinephrine in the anterior lateral thigh is preferred over subcutaneous injection.

Intravenous epinephrine is an option for patients with severe hypotension or cardiac arrest unresponsive to intramuscular doses of epinephrine and fluid resuscitation. Although there is no precisely established dosage or regimen for intravenous epinephrine in anaphylaxis, 5 to 10 mg intravenous bolus (0.2 mg/kg) doses for hypotension and 0.1 to 0.5 mg administered intravenously in the presence of cardiovascular collapse have been suggested. Other treatments should be combined with epinephrine such as: fluid resuscitation, recumbent posture, oxygen, inhaled adrenergic agents, vasopressors, H1 and H2 histamine antagonists, corticosteroids, and glucagon for individuals on  $\beta$  adrenergic blocking agents. (Sampson et al. 2006)

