### **3.2.3 Inclusion Criteria**

**Subjects must meet all of the following criteria at the time of subject ID assignment:**

1. Male or female subjects between 18 and 50 years of age, inclusive
2. Body mass index between 18 and 30 kg/m^2, inclusive
3. Female subjects physically capable of pregnancy (i.e., not sterilized and still menstruating or within 1 year of the last menses if menopausal) must:
  - a. Agree to avoid pregnancy from 28 days prior to Study Day 0 through the duration of the study.

- b. If in a sexual relationship with a man, use an acceptable method of avoiding pregnancy during this period. Acceptable methods of avoiding pregnancy include: the use of at least two forms of contraception, including use by a partner of a barrier method (e.g., male condom with intravaginal spermicide) as one form of contraception.
4. Women of childbearing potential must have a negative serum pregnancy test within 48 hours preceding receipt of the first dose.
5. Can understand and sign the informed consent document, can communicate with the investigator and provide updated contact information as needed for the duration of the study, has no current plans to move from the study area for the duration of the study, and can understand and comply with the requirements of the protocol.

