16. Receipt of immunosuppressive medications other than inhaled or topical immunosuppressant drugs within 45 days prior to Study Day 0
17. Body weight greater than 90 kg.
18. History or evidence of IgA deficiency

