### **3.5.1 SYN023 (Study Drug)**

One or more IM injections of the calculated dose of SYN023 should be administered in any of the acceptable injection sites on the RIGHT side of the body on Study Day 0. If for some reason left sided administrations sites must be used a record must be kept of the site and care taken to not administer SYN023 at a rabies vaccination site. SYN023 is supplied at a concentration of 10 mg/mL. For example a dose calculation for a 70 kg person receiving SYN023 at the dose of 0.3 mg/kg would require a dose of 21mg resulting in a dose volume of 2.1 mL. This would need to be administration into injection sites as described below. A needle no smaller than 21-gauge and 1.0 to 3.0 inches in length depending on subject size should be used to draw up the dose of SYN023. Aspiration of SYN023 from the vial should be done gently to avoid foaming.

SYN023 is to be administered as one or more IM injections in one of three possible injection site: the gluteus medius (ventrogluteal injection site/hip), the vastus lateralis (thigh), rectus femoris (thigh) and the deltoid muscle. Doses of up to 5 mL may be given as a single injection into the hip and thigh muscles. Doses up to 3 mL may be given if required in the deltoid muscle. No more than one injection may be administered into each muscle. Only a single deltoid administration is permitted in any subject. Injections into the gluteus maximus (buttocks) will not be performed.

When selecting the site of injection, known paths of nerves, arteries and veins are to be avoided. If available ultrasound assessment of thickness of fat pad and survey of nerve and blood vessel paths may be employed. The needle should be inserted into the skin at a 90° angle. Before SYN023 is administered, aspirate gently by pulling back on the plunger. If blood is drawn into the syringe, the needle is in a blood vessel and must be moved. Remove the needle from the muscle, re-insert it in a new location in the same muscle, and repeat the aspiration step before administering SYN023. If a dose of SYN023 is drawn up and cannot be administered immediately, the syringe may be stored at 2° to 8° C and used within 3 hours.

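### Protocol 3.6.3.3, as supplied, gives an intravenous epinephrine bolus for hypotension 10 to 100 times the amount for cardiovascular collapse in the same sentence, which indicates a unit fault unless the unit was misread from the PDF

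*Protocol*

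**What the plan says.** Protocol 3.6.3.3 (Treatment of Anaphylaxis) starts with the intramuscular regimen: "Aqueous epinephrine, 0.01 mg/kg (maximum dose, 1.5 mg) administered intramuscularly every 5 to 15 minutes as necessary". It then places intravenous use second: "Intravenous epinephrine is an option for patients with severe hypotension or cardiac arrest unresponsive to intramuscular doses of epinephrine and fluid resuscitation". The amounts follow in one sentence, which opens with a caution, "Although there is no precisely established dosage or regimen for intravenous epinephrine in anaphylaxis", and reports as suggestions "5 to 10 mg intravenous bolus (0.2 mg/kg) doses for hypotension and 0.1 to 0.5 mg administered intravenously in the presence of cardiovascular collapse". The section attributes this advice to a published symposium report on anaphylaxis. Neither the protocol nor the SAP restates or corrects the amounts elsewhere.

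Three other provisions bear on the point:

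- **Weight and build.** Protocol 3.2.4 excludes "Body weight greater than 90 kg". Protocol 3.2.3 asks for "Body mass index between 18 and 30" kg/m² and sets no minimum weight.
- **Worked example.** Protocol 3.5.1 uses a 70 kg subject: "For example a dose calculation for a 70 kg person".
- **Staffing.** Protocol 3.6.3.1 requires that "a medically qualified study team member trained to recognize and treat anaphylaxis must be present in the clinic" throughout vaccination and the observation period.

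**The concern.** One would not expect the sentence to give far more drug for hypotension than for cardiovascular collapse, the graver state. Nor would one expect the intravenous bolus to be many times the intramuscular dose a few lines above it. Neither contrast proves an error alone, because indications and routes can differ. When both point the same way, and the per-kg figures do too, the likeliest explanation is a wrong unit on the hypotension figures.

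The stake is subject safety, not inference. The trial plans to dose 160 healthy volunteers with an antibody product and five vaccine injections each. Protocol 3.6.3.1 treats hypersensitivity as a possible effect of every product, and Protocol 6.2 makes an anaphylactic reaction to SYN023 a stopping event. Section 3.6.3.3 is what site staff might consult in such an emergency, under time pressure.

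**Working it through.** **Inputs.**
- Intramuscular: 0.01 mg/kg, maximum 1.5 mg (Protocol 3.6.3.3).
- Intravenous for hypotension: 5 to 10 mg, glossed as 0.2 mg/kg (same section).
- Intravenous for collapse: 0.1 to 0.5 mg (same sentence).
- Weights: 70 kg example (Protocol 3.5.1) and 90 kg upper limit (Protocol 3.2.4).

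**Step 1. The plan's own equivalence.** The weight at which the gloss equals the range is the range divided by 0.2: 5 / 0.2 = 25 kg and 10 / 0.2 = 50 kg. The pair agrees only from 25 to 50 kg. Above that:
- 70 kg: 0.2 × 70 = 14, and 14 / 10 = 1.4 times the top of the range.
- 90 kg: 0.2 × 90 = 18, and 18 / 10 = 1.8 times the top of the range.

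Both figures carry the same unit, so this result is the same in milligrams and in micrograms.

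**Step 2. Hypotension against collapse, as supplied (mg).** The smallest ratio is 5 / 0.5 = 10 and the largest is 10 / 0.1 = 100.

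**Step 3. Intravenous bolus against the intramuscular dose an eligible subject would receive (mg).**

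| Weight | Intramuscular dose | Bolus / intramuscular dose |
|---|---|---|
| 70 kg | 0.01 × 70 = 0.7 mg | 5 / 0.7 = 7.1 to 10 / 0.7 = 14.3 |
| 90 kg | 0.01 × 90 = 0.9 mg | 5 / 0.9 = 5.6 to 10 / 0.9 = 11.1 |

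Per kg, the ratio is 0.2 / 0.01 = 20 at every weight.

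**Step 4. The same sentence if the hypotension figures were micrograms (an assumption).** The bolus would be 0.005 to 0.010 mg. The collapse amount would then be the larger, by 0.1 / 0.010 = 10 to 0.5 / 0.005 = 100 times. The order in Step 2 reverses, and the excess in Step 3 disappears. The mismatch in Step 1 stays.

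**Step 5. Could the unit be a reading artefact?** The supplied text contains no micro sign as such, so there is no direct test. There are two indirect signs:
- Other Greek letters survived: the beta in the remark on adrenergic blocking agents in 3.6.3.3 itself, and beta, kappa and lambda in the List of Abbreviations.
- Where Appendix E needs a micro prefix, it reads umol/L (creatinine) and ukat/L (CPK). Whether that u was typed or converted is unknown, but in neither place did it become m.

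Both lean towards mg being on the issued page. Neither excludes a misread.

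**The case against.** The strongest objection is that the main point depends on a character this review cannot see. If the issued page prints a microgram unit, the unit fault is an artefact of reading the PDF and not an error in the plan. That stands, and it is why the conclusion is conditional and the first action is a page check. Step 5 reduces the doubt without removing it.

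A second objection is that different routes and indications need not share a dose scale, and the documents give no rule linking them. This is fair for each comparison taken singly. It is weaker against three that agree, one of them within a single sentence.

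Third, the sentence is hedged. Only the intramuscular regimen is recommended, intravenous use comes after intramuscular doses and fluids have failed, and trained staff must be present. All of this limits the risk. It does not make the printed figures coherent.

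Fourth, the per-kg figure may be a separate weight-based suggestion and not a conversion, and it may come unchanged from the cited report. Eligible subjects can also weigh 50 kg or less: at BMI 18, 50 kg corresponds to a height of √(50/18) = 1.67 m. For these reasons the mismatch is a minor looseness only.

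A reader might also compare the bolus with the 1.5 mg intramuscular maximum and quote 5 / 1.5 = 3.3 to 10 / 1.5 = 6.7 times. That is a poor yardstick for this trial. The maximum would bind only at 1.5 / 0.01 = 150 kg, and nobody above 90 kg may enrol. The 0.9 mg dose at 90 kg is the right comparator.

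**Conclusion.** The point holds in conditional form. If the issued page prints mg, the hypotension pair very probably carries a unit fault: 10 to 100 times the collapse amount, 5.6 to 11.1 times the intramuscular dose at 90 kg, and 20 times the intramuscular dose per kg. The available evidence leans towards mg being printed. Separately and as a minor matter, the per-kg gloss exceeds the top of its range by 1.4-fold at 70 kg and 1.8-fold at 90 kg in any unit, if it was meant as a conversion.

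A reader might infer three stronger things that the documents do not support:

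- **That the protocol certainly prints a dangerous dose.** The supplied text cannot settle the unit.
- **That micrograms are the correct unit.** That reading makes the order of the amounts coherent, but the cited report is not available here and no replacement dose is proposed.
- **That the trial's results are at risk.** No endpoint, population, sample size or analysis depends on this sentence.

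It should be fixed because it is safety text in the study procedures and the correction is cheap.

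**What to change.** 1. **Check the unit** of the bolus and of its per-kg figure on the issued page.
2. **If it prints mg:** the sponsor corrects both figures against the symposium report that the section cites. Alternatively, the sponsor deletes the intravenous amounts and leaves intravenous dosing to the trained clinician required by Protocol 3.6.3.1.
3. **Issue it as an amendment.** Protocol 12 requires written sponsor approval and IRB/IEC approval before implementation, so the medical monitor should not simply change the text. If dosing is under way, use the exception in Protocol 9.2 for eliminating an immediate hazard. In either case, notify the site at once.
4. **If it prints micrograms:** only reconcile the per-kg figure with the absolute range, or state the weights to which it applies.

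The cost is one page check and, at most, one short amendment with a site notice. The SAP does not change.

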### **3.6.3.4 Recognition and Evaluation of Immune Complex Illness**

Simultaneous presence of antibodies directed at circulating antigens may result in illness. Immune complex illness (ICI) results from the deposition of antibody-antigen complexes on the microvasculature with the resulting activation of complement and release of inflammatory mediators and tissue injury. These manifestations may result when anti-rabies antibodies such as those in RIG are administered in temporal proximity to rabies vaccine. They may also result when repetitive vaccination induces antibodies to the administered antigens. ICI manifests itself with inflammation and evidence of vascular injury. Syndromes of allergic vasculitis (leukocytoclastic vasculitis or Henoch-schonlein vasculitis in the case of IgA) and glomerular injury may be observed. Clinical manifestations of headache, anorexia and fever occur early followed by a petechial rash (palpable purpura) or larger purpura and cutaneous edema more frequent in the dependent regions of the body. Joint pain, rash and abdominal pain are common. The urinary findings may reflect an active glomerular process with hematuria, proteinuria and RBC casts. Acute glomerular histologic lesions of hypercellularity, necrosis, crescent formation and leukocyte infiltration are seen. Ultimately a reduction in renal function and elevated serum creatinine reflects this glomerular damage. ICI is treated by the cessation of antigen or antibody administration or the suppression of endogenously produced antigen. Prednisone has been used in the treatment of ICI (Salmon 2012).

### **3.6.3.5 Clinical Assessments and Laboratory Tests**

#### **Abnormal Clinical Assessments and Laboratory Tests**

Results from clinical laboratory tests obtained on the study must be reviewed by the investigator (or a designee who is a medically qualified study team member) within 72 hours of receiving the results to determine if abnormalities exist. If the laboratory value is abnormal and has increased in toxicity grade (see Appendix E for toxicity grading scales) from baseline values, it must be reported as an adverse event and repeated promptly to demonstrate resolution. Additional laboratory tests may be performed if the investigator deems them to be necessary to fully evaluate an adverse event. In the event that the investigator elects to order non-protocol-specified laboratory tests, the investigator must record the rationale for the tests and a determination of clinical significance of the result in the source documents. The investigator must keep the medical monitor informed of adverse events of clinical significance.

Abnormal results and findings will be discussed with the subject, or the subject will be referred for follow-up with their healthcare provider if necessary.

### **3.6.3.6 Adverse Events**

The collection periods for adverse events are:

Unsolicited adverse events: 42 days after Study Drug Administration

Solicited adverse events: 28 days after Study Drug Administration

Serious adverse events: Entire study period (i.e., 112 days)

For this study, solicited adverse events are listed in section 5.7.

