**Table 2.2-1 Treatment Allocation**

Treatment Allocation	Number of subjects
RVi + RIG	40
RVa + RIG	40
RVi + SYN023 0.3 mg/kg	40
RVa + SYN023 0.3 mg/kg	40
Total	160

The RVi and RVa regimens for post exposure prophylaxis are both five dose regimens. The initial dose of RVi and RVa will be co-administered with Study Drug (either RIG or 0.3 mg/kg SYN023) on Study Day 0. Rabies virus neutralizing activity (RVNA) and blood levels of SYN023 will be measured for the remainder of the trial while the rest of the post-exposure RVi and RVa doses are given. It is anticipated that RVNA will remain high during RVi and RVa administration and through the end of the study at Study Day 112. Pharmacodynamic efficacy will be defined as RVNA measured above 0.5 IU/mL with RVi and RVa for the duration of the trial and no more than 10% lower for SYN023 compared to RIG at any time point through Study Day 35. SYN023 concentrations and anti-SYN023 antibodies will also be measured.

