**Table 3.1-1 Summary Schedule of Subject Treatment and Evaluations**

Study Visit Day →	Screen	-2	0	1	3	7	14	28	35	42	84	112
Visit Window d		0	0	0	0	1	1	3	4	4	8	11
Written informed consent	X											
Eligibility criteria verification	X											
Medical history	X											
Physical examination	X											
ECG e	X		X	X	X	X	X	X				X
Urine toxicology screen	X											
Urine βHCG (all females) e	X				X	X	X	X				X
Serum βHCG (all females) a		5										
Serum Hepatitis B, C tests	3											
Serum HIV-1,2 tests	3											
Rabies Vaccine administration			X		X	X	X	X				
Study Drug Administration			X									
Urinalysis e	X		X	X	X	X	X	X	X	X		X
Serum Anti-rabies activity e			10	10	10	10	10	10	10	10	10	10
Serum chemistry b,c	10		10	10	10	10	10	10				10
CBC, differential, platelets e	7		7	7	7	7	7	7				7
PT (INR), PTT e	5		5			5						5
Serum IgA	7											
SYN023 Pharmacokinetics e			14	7	7	7	7	7	7	7	7	
Anti-SYN023 antibodies e			5			5	5	5	5	5	5	5
Weight	X		X									X
Vital signs & oximetry	X		X	X	X	X	X	X				X
Interval history			X	X	X	X	X	X	X	X	X	X
Focused physical examination			X	X	X	X	X	X	X	X	X	X
Solicited adverse events (incl. con. meds.)			X	X	X	X	X	X				
Unsolicited adverse events (incl. con. meds.)			X	X	X	X	X	X	X	X		
Serious adverse events (incl. con. meds.)			X	X	X	X	X	X	X	X	X	X
Site of injection examination			X	X	X	X	X	X	X	X		X
Lymphadenopathy			X	X	X	X	X	X	X	X		X
Per visit phlebotomy volume	35	5	51	34	34	39	39	39	22	22	22	37
Cumulative phlebotomy volume e	35	40	91	125	159	198	237	276	298	310	332	369

- Results must be known before Study Drug administration
- Serum Chemistry: creatinine phosphokinase (CPK), troponin, total bilirubin, AST, ALT, ALP, creatinine, blood urea nitrogen, sodium, potassium, chloride, bicarbonate, calcium. Note minimum serum chemistry labs for screening visit are: AST, ALT, ALP and creatinine although other labs monitored for safety may be collected if part of panel.
- The cumulative phlebotomy volume is approximate.
- Visit window refers to acceptable variation in days either early or late from scheduled visits in without a protocol violation.
- Must be obtained on day of visit but prior to any injections.

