### **7.6.1 Adverse Events**

The safety profile of SYN023 will be described by treatment group. The primary variable for evaluation of the safety profile will be the number and percentage of unsolicited and solicited adverse events recorded at all available post-vaccination time points. For all presentations of adverse events, additional summaries based on reporting period of adverse events following each study vaccination may also be presented.

The number (percentage) of subjects with adverse events will be summarized by MedDRA system organ class (SOC) and preferred term (PT). Additional summaries will present the number (percentage) of subjects with adverse events by severity and by relationship to study drug; each subject will be counted once per preferred term at the greatest severity or most related state recorded for that term.

Separate summaries of the number (percentage) of subjects with solicited adverse events will also be presented. Solicited adverse events will also be summarized by severity and relationship to study drug; each subject will be counted once per preferred term at the greatest severity or most related state recorded for that term.

In addition, dose-safety curves may be produced to examine the proportion of subjects who experience adverse events by treatment regimen.

Serious adverse events will be recorded through the final study visit for all subjects. Listings will be provided for subjects with serious adverse events.

Listings will be provided for subjects who have discontinued prematurely due to an adverse event.

The number (percentage) of subjects with post-vaccination clinical laboratory values or vital sign values recorded as newly abnormal following study vaccination and meeting toxicity mild

criteria (Grade 1) or above as specified in the Toxicity Table (Appendix E) will be tabulated at each post-vaccination time point and overall. Clinical laboratory and vital sign abnormalities will also be reported as adverse events and will be included in the summary of adverse events.

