9.2.1 Solicited Adverse Events and Injection Site Reactions

Solicited AEs will be events the subject is specifically asked about. These AEs are commonly observed soon after injection of study antibody. The solicited AE reporting period begins with the day of vaccination (Day 0) through Day 28 inclusively. Solicited local AEs to be collected include the following: injection site (s) pain, tenderness, redness swelling, warmth, skin disruption and regional lymphadenopathy. Non-local solicited AEs include headache, arthralgia, myalgia, rash, pruritus, urticaria, dyspnea, chest pain, cough, fever and chills. Solicited AEs of local injection site reactions (i.e., pain at injection site, redness at injection site, or swelling at injection site) will be considered causally related to study vaccine (adverse reaction).

Summary of descriptive statistics for solicited AEs (incidence of subjects with percentages and incidence of solicited AEs) will be presented by treatment and overall, SOC, PT, by investigator-assessed relationship (Not Related, Unlikely Related, Possible, Probable, and Definite) and

severity (Mild, Moderate, and Severe). For incidence of subject calculations, each subject may only contribute once to each of the incidence rates, for a solicited AE following a given treatment, regardless of the number of occurrences; the highest severity or highest relationship will be presented, as appropriate.

In each table, SOC will be presented in descending order of overall incidence rate in terms of frequency of subjects and then in frequency of events (alphabetical order will be used in case of equal rates). For each SOC, PT will be presented the same way.

All solicited AEs will be listed.

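### Solicited collection ends on Day 28, the scheduled day of the fifth vaccine dose, so that dose has at most same-day solicited data

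*Protocol*

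**What the plan says.** **Anchor of the solicited period.** Protocol 3.6.3.6 gives "Solicited adverse events: 28 days after Study Drug Administration" and, for the rest, "Unsolicited adverse events: 42 days after Study Drug Administration". Protocol 2.2 places Study Drug on Day 0 only: "The initial dose of RVi and RVa will be co-administered with Study Drug (either RIG or 0.3 mg/kg SYN023) on Study Day 0". SAP 9.2.1 agrees on the dates: "The solicited AE reporting period begins with the day of vaccination (Day 0) through Day 28 inclusively". In Table 3.1-1 the row "Solicited adverse events (incl. con. meds.)" is marked at Days 0, 1, 3, 7, 14 and 28 and not afterwards.

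**Vaccine schedule.** Protocol 3.5.3, for RVa, says "Five doses of the vaccine should be administered on Study Days 0, 3, 7, 14 and 28". Protocol 3.5.4 and SAP 3.3 give the same days for RVi.

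**What else stops at Day 28.** Protocol 5.15 ties daily home temperature, taken on waking, to the solicited period. Protocol 5.7 ends active evaluation of injection-site ulceration and axillary nodes at Day 28. No end date is given for the diary (Protocol 5.2 and Appendix A).

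**What continues.** Unsolicited events are collected to Day 42 and serious events to Day 112. Table 3.1-1 schedules interval history, focused examination, injection-site examination, lymph-node assessment and urinalysis at Days 35 and 42. SAP 9.2.2 re-records a solicited event that persists beyond Day 28 as unsolicited.

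**The concern.** The solicited period is counted from the antibody, but the products that provoke local and systemic reactions include a vaccine given five times. The end of the period coincides with the last of those doses. Comparing the safety of the two vaccines given with RIG or SYN023 is a secondary objective, and Protocol 7.6.1 makes solicited and unsolicited events together the primary safety variable. The same section says that "additional summaries based on reporting period of adverse events following each study vaccination may also be presented". If such summaries are produced, dose 5 cannot be set beside doses 1 to 4 on solicited events.

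The protocol itself gives a reason to look after the later doses. Section 3.6.3.4 warns that repeated vaccination may lead to immune complex illness, and names headache, fever, joint pain and rash among its signs. All four correspond to solicited terms in Section 5.7. Dose 5 is the most repeated exposure.

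**Working it through.** This is schedule arithmetic; no power or alpha calculation applies.

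**1. The plan's own figure.** Day 0 + 28 days = Day 28. This reproduces Protocol 3.6.3.6 and matches the last solicited mark in Table 3.1-1 and the inclusive end in SAP 9.2.1.

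**2. Days remaining after each dose.** Solicited days after the dose day = 28 − dose day; unsolicited days = 42 − dose day. Table 3.1-1 defines the window thus: "Visit window refers to acceptable variation in days either early or late from scheduled visits". It is 0 days for Days 0 and 3, ±1 for Days 7 and 14, and ±3 for Day 28. The ranges move the dose within its window and hold the end date at Day 28 or Day 42.

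| Dose | Day | Solicited days after dose (range) | Unsolicited days after dose (range) |
|---|---|---|---|
| 1 | 0 | 28 | 42 |
| 2 | 3 | 25 | 39 |
| 3 | 7 | 21 (20 to 22) | 35 (34 to 36) |
| 4 | 14 | 14 (13 to 15) | 28 (27 to 29) |
| 5 | 28 | 0 (−3 to +3) | 14 (11 to 17) |

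On a strict calendar reading, a compliant dose 5 on Days 29 to 31 falls after the period has closed. One on Days 25 to 27 gains one to three days.

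**3. Allowing for overlap.** The 28 days after dose 1 also contain doses 2 to 4. Counting only to the next dose gives 3 − 0 = 3, 7 − 3 = 4, 14 − 7 = 7 and 28 − 14 = 14 days for doses 1 to 4, all within the solicited period. Dose 5 still has 0. The contrast does not depend on how overlap is handled.

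**4. Share of injections.** 160 subjects × 5 doses = 800 planned vaccine injections; 160 / 800 = 20%.

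**5. Temperature and blood tests after dose 5.** Home temperature is taken on waking, so at a Day 28 visit on schedule the last reading precedes the injection. In Table 3.1-1 the next scheduled vital signs after Day 28 are at Day 112. Section 3.1 requires blood to be drawn before any injection, so Day 28 chemistry and blood count also precede dose 5, and the next are at Day 112. Urinalysis is repeated at Days 35 and 42.

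**6. How an event changes class by date.** Redness that begins on Day 28 after dose 5 is solicited and, under Protocol 5.7 and SAP 9.2.1, is treated as causally related. If it persists, SAP 9.2.2 carries it over as unsolicited. The same redness beginning on Day 29 appears only among unsolicited events, and the automatic causality rule is not stated to apply to it.

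**The case against.** **Dose 5 is followed up.** This stands. Day 28 is included in the period, and the Study Abstract requires a look at the site 30 minutes after every injection. Protocol 3.6.3.1 has subjects asked about new symptoms at every clinical contact, and the examinations at Days 35 and 42 fall about 7 and 14 days after the dose. A reader might infer that dose 5 has no follow-up, or that later reactions surface only if volunteered. The documents do not support either. What is missing is the itemised list and the daily temperature.

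**The visit window may move collection with the dose.** This partly stands. Protocol 5.7 refers to Table 3.1-1 for the solicited period, and the table marks dose 5 and the solicited assessment at the same visit. If that visit moves to Day 31, the assessment can move too. A late dose falls wholly outside collection only on the calendar wording of Protocol 3.6.3.6 and SAP 9.2.1. On either reading, nothing solicited is scheduled after that visit.

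**The anchor is a design choice.** Section 5.7 describes solicited events as typical soon after the study antibody, which is given once, and the vaccines are licensed. That explains the Day 0 anchor, but neither document gives it as a reason for omitting dose 5, and the safety objective names the vaccines.

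**No per-dose table is promised.** This stands. Protocol 7.6.1 makes per-vaccination summaries optional, and SAP 9.2.1 specifies none. A reader might infer that the report will show falsely low dose 5 rates; no planned output would do so.

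**Conclusion.** The point holds as a gap in description. Given on schedule, the fifth vaccine dose, 160 of 800 planned injections, has at most same-day solicited data, against 14 to 28 days for doses 1 to 4. Read by the calendar, it has none if given late but in window. Reactions beginning on Day 29 or later can still be recorded, but by a different method and in different tables.

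A reader might go further and infer that the cutoff distorts the comparison of RIG with SYN023. The documents do not support this: the vaccine days and the cutoff are the same in all four arms, so the cutoff does not by itself create a bias between them. Nor do they state that the diary ends on Day 28; only temperature is expressly tied to the solicited period.

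The 20% is a count of injections, not an estimate of missed reactions. The documents give no reaction rate after dose 5 and no figure for how much less general inquiry detects than an itemised list, so the number of events affected cannot be estimated. The result assumes full enrolment of 160 and all five doses given. This is an inexpensive improvement; it is not a flaw that threatens the trial's conclusions.

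**What to change.** Extend the itemised solicited review and home temperature through the existing Day 35 visit, and state the same end date for the diary. At scheduled visits this gives 35 − 28 = 7 days after dose 5. If the end is fixed at calendar Day 35, the range with the Day 28 window is 35 − 31 = 4 to 35 − 25 = 10 days, so the text should say whether collection ends on the calendar day or at the visit.

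Change together:
- Protocol Study Abstract (Analysis of Safety), 3.6.3.6, 5.7 and 5.15, and the solicited row of Table 3.1-1;
- SAP 9.2.1 (reporting period) and 9.2.2 (the date after which a persisting solicited event becomes unsolicited).

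In the same amendment, reconcile Protocol 5.7, which ends active site and node evaluation at Day 28, with Table 3.1-1, which schedules site and node examinations at Days 35, 42 and 112.

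**Cost.** About seven more diary and temperature days per subject (7 × 160 = 1,120 subject-days), plus a protocol and SAP amendment with the IRB/IEC approval that Protocol Section 12 requires. No new visit or blood draw is needed. If collection cannot be changed, the SAP should say that the solicited tables cover dose 5 on its scheduled day only, and that any per-vaccination summary of solicited events excludes that dose.
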